**Table 4-1 Analysis Populations**

Population	Definition	Study Intervention
mITT Population	All randomized participants who receive study intervention and who have at least one postintervention investigator-rated FWS measurement at maximum frown	As treated
Safety Population	All participants who receive study intervention	As treated

## 5. Statistical Analyses

### 5.1. General Considerations

- The primary analyses will be performed after the database is locked and randomization schedule is released.
- The effectiveness endpoints will be analyzed based on the mITT Population. Safety analyses will be performed using the Safety Population. The analyses will be based on the actual study intervention that the participants receive.
- For each cohort, the effectiveness and safety endpoints will be analyzed/summarized by study intervention group, i.e., AGN-151586 group and placebo group, respectively. In addition, placebo groups across cohorts will be pooled to compare with each dose of AGN-151586 group as a sensitivity analysis.
- For applicable effectiveness and safety endpoints, baseline is defined as the last non-missing assessment prior to study intervention.
- Descriptive statistics for continuous variables include the sample size (N), mean, standard deviation, median, 1st and 3rd quartiles, minimum, and maximum. Summary statistics for categorical variables include the sample size (N), frequency count, and percentage.
- The primary analysis of the effectiveness endpoint, ie, the response rate of the participants with achievement of a  $\geq 2$  grade improvement from baseline on the FWS according to investigator assessments of GL severity at maximum frown at any postintervention timepoint through Day 7, will be analyzed using CMH tests stratified by baseline GL severity at maximum frown, to compare the between-group difference. The observed data without imputation will be used. Nominal p-values will be provided for each statistical testing. No multiplicity adjustment will be performed to control overall type I error.
- Summary of TEAEs, medical history, and concomitant medication will be summarized by study intervention group for each cohort. Also, the AGN-151586 groups across cohorts and the placebo groups across cohorts will be pooled.
- Partial dates will be treated as missing in computations, and will be listed in the data listings as they appear on the electronic case report form (eCRFs). No imputation of missing values will be performed, unless otherwise specified.
- The level of significance used for statistical testing of the effectiveness endpoints will be 0.05, 2-sided.

- The change from baseline values will be computed as the value for the postbaseline visit minus the baseline value.
- All statistical analysis will be performed using SAS version 9.4 or higher.
- Medical dictionary for regulatory activities (MedDRA) version 23.0 or higher will be used to code AEs and medical history.
- World Health Organization (WHO) Drug Dictionary will be used to code medications.
- Due to the COVID-19 pandemic, randomization into the study was curtailed for Cohort 3 only (38 of 40 participants randomized into Cohort 3), and visit assessments were modified for Cohorts 3 & 4 only. For Cohort 5, participants were expected to complete the visits as per the protocol; hence, no modifications were made to the visits for Cohort 5. These changes will be reported as a listing for modified visits due to COVID-19-related reasons.

## **5.2. Participant Disposition**

The number of participants in the study populations (mITT and Safety) will be summarized by study intervention group; the number of participants screened will be summarized overall.

Summary of study disposition will be provided by study intervention group for the following:

- Number of randomized participants
- Number of participants who receive study intervention
- Number of participants who discontinue the study
- Reasons for discontinuation of the study

## **5.3. Primary Effectiveness Endpoint Analysis**

### **5.3.1. Definition of Endpoint**

The assessments of the severity of GL at maximum frown using the validated FWS, is based on the following scale:

- 0 = None
- 1 = Mild
- 2 = Moderate
- 3 = Severe

If a participant is determined to have at least a 2-grade improvement from baseline by the investigator-rated FWS at maximum frown at any postintervention assessment through Day 7, he/she will be considered as a responder. The primary effectiveness endpoint is the response rate of the participants with achievement of a  $\geq$  2-grade improvement from baseline on the FWS according to investigator assessments of GL severity at maximum frown at any postintervention timepoint through Day 7.

### **5.3.2. Main Analytical Approach**

The proportion of responders for the primary endpoint will be analyzed based on mITT Population using CMH tests stratified by investigator assessment of baseline GL severity at maximum frown to compare each AGN-151586 study intervention group versus placebo for each cohort. In addition, placebo groups across cohorts will be pooled. Each AGN-151586 group will be compared against the pooled placebo groups as a sensitivity analysis. The observed data without imputation will be used.

The response rates of the participants with achievement of a  $\geq$  2-grade improvement from baseline on the FWS according to investigator assessments of GL severity at maximum frown at any postintervention timepoint through Day 7 will be calculated for each study intervention group. The corresponding 95% confidence intervals (CIs) using normal approximation (ie, Wald) will be provided.

The proportion difference, the corresponding Wald 95% CIs and nominal p-values will be provided for the comparison of response rates in the primary endpoint between different study intervention groups. P-values will be calculated based on the stratified CMH tests, but the rate differences are presented without stratification.

The p-values presented for each statistical test are deemed nominal. No multiplicity adjustment will be performed to control the overall Type I error.

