9.2. Sample Size Determination

For each cohort, there will be approximately 40 participants (AGN-151586: n = 30; placebo: n = 10) with a 3:1 randomization allocation; up to 5 dose cohorts are planned. For a cohort of 30 participants treated with AGN-151586, there is an approximately 60% chance of detecting an adverse event which occurs at a 3% incidence (eg, eyelid ptosis).

Approximately 200 participants will be randomized to have approximately 180 participants complete the study based on an anticipated dropout rate of 10%. Approximately 150 participants are expected to have a single dose exposure to AGN-151586 with an approximately 78% chance to detect any adverse event at a 1% incidence, and a 95% chance to detect any adverse event at a 2% incidence.

The primary efficacy analysis will be conducted on the mITT population, which consists of randomized participants who have been dosed and have a posttreatment measurement of investigator-rated FWS at maximum frown. A sample size of 40 participants per cohort will have approximately 87% power to detect a difference between an AGN-151586 dose group and the placebo group, assuming a 10% dropout rate and responder rates of 70% for the AGN-151586 study intervention group and 10% for the placebo group.

The calculation is based on a 2-sided Chi-squared test (Fisher's exact test) with a 0.05 significance level using nQuery Advisor version 7.0.

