### 3. Sample Size Determination

The primary efficacy analysis will be conducted on the mITT Population, which consists of randomized participants who have received study intervention and have at least one postintervention measurement of investigator-rated FWS at maximum frown. A sample size of 40 participants per cohort will have approximately 88% power to detect a difference between an AGN-151586 dose group and the placebo group, assuming a 5% dropout rate and responder rates of 70% for the AGN-151586 study intervention group and 10% for the placebo group. The calculation is based on a 2-sided Chi-squared test (Fisher's exact test) with a 0.05 significance level using nQuery Advisor version 7.0.

For each cohort subset data reviewed by the DMC, beginning with the lowest dose before progressing to higher doses, the study will have increasing power to detect AE incidence among the participants treated with AGN-151586. For Cohort 1 DMC review, for example, with a subset of 12 participants treated with AGN-151586, there will be approximately 72% chance to detect an AE at a 10% incidence. For subsequent cohorts with increasing doses, for example, with subsets of 21 participants treated with AGN-151586, there will be approximately 90% chance to detect an AE at 10% incidence. A table is included below to show the range of probabilities of detecting AEs with varying incidence rates.

TRUE EVENT RATE (%)	12 on Active Treatment	21 on Active Treatment	30 on Active Treatment	60 on Active Treatment
0.5%	0.06 (0, 0.19)	0.10 (0, 0.23)	0.14 (0.02, 0.26)	0.26 (0.15, 0.37)
1%	0.11 (0, 0.29)	0.19 (0.02, 0.36)	0.26 (0.10, 0.42)	0.45 (0.33, 0.58)
3%	0.31 (0.05, 0.57)	0.47 (0.26, 0.69)	0.60 (0.42, 0.77)	0.84 (0.75, 0.93)
5%	0.46 (0.18, 0.74)	0.66 (0.46, 0.86)	0.79 (0.64, 0.93)	0.95 (0.90, 1)
10%	0.72 (0.46, 0.97)	0.89 (0.76, 1)	0.96 (0.89, 1)	>0.99 (0.99, 1)
20%	0.93 (0.79, 1)	0.99 (0.95, 1)	>0.99 (0.99, 1)	>0.99 (0.99, 1)
30%	0.99 (0.92, 1)	>0.99 (0.99, 1)	>0.99 (0.99, 1)	>0.99 (0.99, 1)
50%	>0.99 (0.99, 1)	>0.99 (0.99, 1)	>0.99 (0.99, 1)	>0.99 (0.99, 1)

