#### **5.4.2. Main Analytical Approach**

The responder analyses will be analyzed in a similar way as for the primary effectiveness endpoint. The nominal p-values based on secondary effectiveness endpoints will be considered as supportive.

Descriptive statistics including the sample size (N), mean, standard deviation, median, 1st and 3rd quartiles, minimum, and maximum will be summarized by study intervention group and timepoint using the mITT Population for the FLO-11 item scores and total score, FLSQ item scores and domain scores.

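### Wald 95% intervals for cohorts of about 30 active and 10 placebo participants cover about 89% at the planning rates, and the placebo interval is [0, 0] in about one cohort in three

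*SAP*

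**What the plan says.** SAP 5.3.2 names the interval method twice. For the response rate in each group: "The corresponding 95% confidence intervals (CIs) using normal approximation (ie, Wald) will be provided". For the comparison between groups: "The proportion difference, the corresponding Wald 95% CIs and nominal p-values will be provided". The interval for the difference is unstratified, although the test is stratified: "P-values will be calculated based on the stratified CMH tests, but the rate differences are presented without stratification".

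Protocol 9.2 plans 30 active and 10 placebo participants per cohort and assumes "responder rates of 70% for the AGN-151586 study intervention group and 10% for the placebo group". On attrition, the protocol power statement is made "assuming a 10% dropout rate" and SAP section 3 is written "assuming a 5% dropout rate". Protocol 9.4.1.2 asks for two-sided 95% intervals for the difference without naming a method. Wald is therefore the SAP's choice, and the SAP version history lists it as a clarification.

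SAP 5.4.2 extends the approach to the secondary endpoints: "The responder analyses will be analyzed in a similar way as for the primary effectiveness endpoint". Most of these are assessed by timepoint. Comparison with placebo pooled across cohorts is planned as a sensitivity analysis only. The readable text contains no small-sample interval and no rule for zero responders.

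**The concern.** The Wald interval estimates each arm's variance as p(1 - p)/n at the observed proportion. With about one responder expected among 10 placebo participants, that estimate is unstable, and with none it is exactly zero. The placebo arm matters here: at 70% versus 10% it contributes 0.10 × 0.90/10 = 0.009 to the variance of the difference, against 0.70 × 0.30/30 = 0.007 from the active arm. A cohort with 0/10 on placebo therefore loses the larger variance component just when the observed difference is at its most favourable. The interval is then too narrow and placed too high.

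At stake is how well the effect at each dose appears to be known in a study whose data are meant to inform later dose selection (protocol 4.3). A printed interval may also disagree with the p-value beside it.

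**Working it through.** **Inputs.** Arms of 30 and 10 and rates of 70% and 10% (protocol 9.2); dropout of 10% (protocol 9.2) or 5% (SAP section 3); two-sided 0.05.

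**The plan's own figures.** Continuity-corrected chi-squared power is Φ{[Δ - c - 1.96 √(p̄(1 - p̄)(1/n₁ + 1/n₂))] / √(p₁q₁/n₁ + p₂q₂/n₂)}, with q = 1 - p and c = ½(1/n₁ + 1/n₂).
- 10% dropout, 27 and 9: p̄ = (18.9 + 0.9)/36 = 0.55 and c = 0.074, so (0.600 - 0.074 - 0.375)/0.133 = 1.13 and power is 87.1%. The protocol states 87%.
- 5% dropout, 29 and 9: 88.2% (Fisher's exact 88.8%). The SAP states 88%.

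The planning inputs are therefore read as the documents intend.

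**Placebo-rate interval.** The formula is p̂ ± 1.96 √(p̂(1 - p̂)/10). At a true rate of 10%:
- 0/10 has probability 0.9¹⁰ = 34.9% and gives [0, 0].
- Only 1, 2, 3 or 4 responders give an interval containing 10%: 38.7% + 19.4% + 5.7% + 1.1% = 65.0% coverage, rounding aside.
- With 1 or 2 responders (58% probability) the lower limit is below zero.
- With 9 evaluable, coverage is 60.4% and P([0, 0]) = 0.9⁹ = 38.7%.
- Over five independent cohorts of 10, 5 × 0.349 = 1.7 are expected to show [0, 0], and the chance of at least one is 1 - (1 - 0.349)⁵ = 88%.
- At other assumed placebo rates, P([0, 0]) is 59.9% (rate 5%) or 10.7% (rate 20%).

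**Interval for the difference.** The formula is d ± 1.96 √(p̂₁(1 - p̂₁)/n₁ + p̂₂(1 - p̂₂)/n₂). Coverage is the sum of the binomial probabilities of all outcomes whose interval contains the true difference.

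| Arms | True rates (active/placebo) | Wald coverage |
|---|---|---|
| 30/10 | 70/10 | 89.2% |
| 29/10 | 70/10 | 87.6% |
| 28/9 | 70/10 | 90.4% |
| 27/9 | 70/10 | 88.9% |
| 30/10 | 10/10 | 86.9% |
| 30/10 | 30/10 | 93.2% |
| 30/10 | 50/10 | 92.0% |
| 30/10 | 90/10 | 84.9% |
| 30/10 | 5/5 | 96.1% |
| 30/50 (pooled placebo) | 70/10 | 92.8% |

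At 30/10 and 70/10, the interval lies wholly above the truth in 9.9% of cohorts and wholly below it in 0.9%. On the same outcomes Newcombe covers 95.1% and Miettinen-Nurminen 96.3%.

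**Single data sets.**
- 21/30 v 0/10: Wald is 0.70 ± 1.96 √0.007 = [0.536, 0.864]; Newcombe is [0.370, 0.833]. The lower limits differ by about 17 percentage points.
- 4/30 v 0/10: Wald is [0.012, 0.255], which excludes zero. Newcombe is [-0.156, 0.297], Fisher's p is 0.56 and the unstratified CMH p is about 0.23.
- 0/30 v 0/10: Wald is [0, 0]; Newcombe is [-0.278, 0.114].

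**The case against.** The strongest reply is that these intervals decide nothing. SAP section 2 tests the hypothesis with the stratified CMH test, the p-values do not use the intervals, and escalation is a DMC judgement on selected safety and efficacy data. This stands. A reader might infer that the intervals are the main basis for choosing a dose, but no section ties dose choice or success to a confidence limit.

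A reader might also take one further result as a false-positive rate: with 10% in both arms, the Wald interval excludes zero in 13.1% of cohorts. It is a property of the interval, not the trial's type I error. CMH rejects in about 2.8% of such cohorts (assuming 15 active and 5 placebo per stratum, with equal rates). What the 13.1% does show is that the interval and the p-value can disagree.

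The shortfall also depends on unknown rates. Randomization is stratified by severity, and a two-grade gain from moderate requires a final grade of none, so response probably differs by stratum. With assumed stratum rates of 50%/90% active and 5%/15% placebo, coverage rises to 90.6%; with 0%/20% placebo it is 91.2%. The shortfall shrinks but remains.

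The pooled-placebo comparison is a real mitigation: 92.8% coverage, with [0, 0] very unlikely at up to 50 participants. It is only a sensitivity analysis and leaves the primary within-cohort display as it is. Finally, a [0, 0] interval printed beside 0/10 is visibly degenerate. The too-narrow interval for the difference next to it is less obvious.

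**Conclusion.** The interval method is wrong as written for these arm sizes and should be changed. It is a fault in reported precision in a phase 2b study, not a threat to the primary test. The main figures assume independent binomial outcomes at the documents' planning rates.

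It would go too far to say that the intervals always under-cover, or that [0, 0] is the usual result. Coverage can reach or exceed 95% at some rates, and [0, 0] is the minority case at a 10% placebo rate. It also concerns the single-arm interval. The interval for the difference collapses only when each arm is at 0% or 100%. That can happen at early timepoints, such as Hour 4, under SAP 5.4.2; how often cannot be computed, because the documents give no expected early response rates.

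**What to change.** In SAP 5.3.2, and by reference in 5.4.2, replace Wald with Newcombe or Miettinen-Nurminen score intervals for differences in response rates, and with Wilson or Clopper-Pearson intervals for single rates. Name one method for each purpose. At 10 participants and a 10% rate, Wilson covers 93.0% and Clopper-Pearson 98.7%. For 0/10 they give [0, 0.278] and [0, 0.308].

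The cost is one SAP sentence and an option change in SAS 9.4, which SAP 5.1 already specifies. Design, sample size and test stay as they are. Some intervals become wider. The replacements are not perfectly balanced either: at 29/10 and 70/10, Newcombe's misses are nearly all below the true difference (4.8%, against 0.1% above), so its errors are on the cautious side. An unstratified interval can still occasionally disagree with a stratified p-value, and a table footnote should say so.

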9.4.1.2. Primary Efficacy Analyses

The purpose of the primary analyses is to test for the primary endpoint, that is, the achievement of $a \ge 2$ -grade improvement in FWS according to investigator assessments of GL severity at maximum frown from Day 1 through Day 7 for each cohort. Safety will be assessed by the DMC.

- The purpose of the primary analyses will be to test for the primary endpoint (ie, at least a 2-grade improvement response from investigator) during any timepoint after study intervention administration through Day 7 for each AGN-151586 intervention dose group versus placebo group for each cohort. For example, if it is determined by the investigator-rated FWS that participants have at least a 2-grade improvement at any postintervention assessment through Day 7, they will meet the responder definition for each assessment timepoint this applies.
- The proportion of responders for the primary endpoint for each AGN-151586 study intervention group versus placebo will be analyzed using CMH tests stratified by baseline GL severity at maximum frown, using observed data without imputation or adjustment for multiplicity. In addition, 2-sided 95% CIs for the treatment differences in response rates will be provided. Between group comparisons will only be performed for each AGN-151586 group against the placebo group. Nominal p-values will be presented for each statistical test.
- Observed data without imputation will be used with stratification based on baseline GL severity for the primary analysis described above. In addition, sensitivity analyses of the primary efficacy variable will be performed to establish consistency and robustness and further characterize the extent of participants' responses (eg, missing as nonresponder). In addition, placebo groups across cohorts can be pooled to compare with each AGN-151586 group as a supportive analysis. Details will be provided in the SAP.

AGN-151586

Baseline and posttreatment values will be summarized using descriptive statistics for the AGN-151586 dose groups and placebo group for each cohort at each assessment timepoint. Details will be provided in the SAP.

The safety analysis will be performed using the safety population and will be defined in the SAP. The safety parameters will include:

- Incidence of adverse events, including adverse event severity and causality as assessed by the investigator

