## SAP Version History

This Statistical Analysis Plan (SAP) Amendment 1 for study 2034-201-008 is based on the Protocol Amendment 1 (dated 05 June 2020).

In addition to minor typographical corrections, other updates from the previous SAP version 1.0 (dated 15 November 2019) include the following:

- Section 1.1: Objectives and Endpoints table added based on objectives and endpoints stated in previous SAP. Estimand framework table updated [REDACTED].  
[REDACTED].
- Section 5.1: SAS version and MedDRA version updated to current versions. Added information about COVID-19-related reasons for modified visits to be reported as a listing.
- Section 5.3.2: Clarification provided for 95% confidence intervals that will be computed using the normal approximation (ie, Wald). In addition, p-values will be based on the stratified CMH tests, but the rate differences are not based on stratification.
- [REDACTED]  
[REDACTED]  
[REDACTED]
- Section 5.5: Added that study period (prior to, during, after study intervention administration) will be presented for safety data listings.
- Section 5.5.2: Added a breakdown for treatment-related AEs to consist of study drug-related AEs and study procedure-related AEs. In addition, PDSOTs will be summarized as part of the overall AE table. Removed from summary the TESAEs leading to study discontinuation. Neurologic assessments will be summarized using descriptive statistics, and a listing will be provided. Treatment-emergent neurologic assessment-related AEs will also be presented by SOC and PT.
- Section 5.6.1: Updated immunogenicity analysis planned summary and stated that the results would be summarized if ready by time of the immunogenicity database lock.
- Sections 5.7 & 5.8: Stated that interim analyses are not applicable to the study, and the DMC analyses were moved to a separate section.
- Section 6.2: Added that a change to the protocol-specified analyses would be the summarization of TEAEs, not just AEs, per the primary safety endpoint.

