## 1.2. Study Design

- This is a multicenter, double-blind, randomized, placebo-controlled, dose-escalation study to evaluate the safety and efficacy of a single study intervention cycle of AGN-151586 in participants with moderate to severe GL.
- Participants are adults 18 to 65 years old, with moderate to severe GL at maximum frown (as assessed by the investigator and participant using the FWS).
- Up to 5 doses of AGN-151586 will be evaluated and compared with placebo in a sequential cohort design, starting with the lowest dose.
- Each cohort will enroll a balanced distribution of participants with moderate or severe GL severity at maximum frown per investigator assessment (at least 40% and no more than 60% of either).
- The primary efficacy measure is the investigator's assessments of GL at maximum frown using the FWS.
- Participants will undergo a Screening Visit up to 30 days before randomization on Day 1. All screening data must be available to the investigator prior to randomization on Day 1.
- On Day 1, participants will be randomly assigned in a 3:1 ratio to receive AGN-151586 or placebo. Enrollment stratification will be by baseline GL severity at maximum frown, assessed by the clinician (principal investigator or physician subinvestigator) using the FWS.
- Study intervention on Day 1 will be administered as 5 injections in the glabellar complex (1 in the procerus and 2 in each corrugator).
- Participants will remain in the clinic for the first 12 hours after administration of study intervention for serial assessments at Hours 4, 8 and 12. Thereafter, participants return to the clinic on Day 2 (Hour 24 and Hour 36), Day 3 (Hour 48 and Hour 60), Day 7, Day 14, Day 21, Day 28, Day 35, and Day 42.
- For each dose group, an internal data monitoring committee (DMC), independent from the study team, will review select safety and efficacy data from a subset of participants ( $n \geq 16$ ) with data through 14 days postintervention (in addition to cumulative data from the prior cohort[s]).
- The DMC may recommend proceeding with the nominal dose for the next cohort, request additional data (eg, data from additional participants in the cohort, data from visits after Day 14), request to repeat the current dose or a lower dose, request an intermediate dose be evaluated (between the dose of the current cohort and the nominal dose for the next cohort), or request dose escalation be terminated.

The study scheme is as follows:

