### **5.3.3. Sensitivity Analysis**

Sensitivity analyses of the primary efficacy variable will be based on the non-responder imputation (NRI) method. If a participant does not have the valid investigator-rated FWS assessment at maximum frown at any postintervention assessment through Day 7, he/she will be considered as a non-responder. CMH tests stratified by baseline investigator assessment of GL severity at maximum frown will be used for the analysis based on the imputed data. In addition, the pooled placebo group will be compared to each AGN study intervention group for proportion differences for the primary analysis.

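### The primary p-value is stratified by baseline severity, but the rate difference and Wald interval beside it are not, so estimate and test can disagree

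*SAP*

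**What the plan says.** SAP 5.3.2 tests the primary endpoint with "CMH tests stratified by investigator assessment of baseline GL severity at maximum frown". For the effect size, "The proportion difference, the corresponding Wald 95% CIs and nominal p-values will be provided", and then: "P-values will be calculated based on the stratified CMH tests, but the rate differences are presented without stratification". The SAP Version History lists the same choice as a clarification made in Amendment 1: "p-values will be based on the stratified CMH tests, but the rate differences are not based on stratification". Protocol 9.4.1.2 asks only that "2-sided 95% CIs for the treatment differences in response rates will be provided" and does not say whether they are stratified.

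Severity is the randomisation factor (SAP 1.2): "Enrollment stratification will be by baseline GL severity at maximum frown". Each cohort may hold "at least 40% and no more than 60% of either" grade. SAP 5.3.3 adds that "the pooled placebo group will be compared to each AGN study intervention group for proportion differences for the primary analysis". SAP 5.4.2 analyses the secondary responder endpoints in a similar way. No stratified effect estimate appears in the visible text of SAP 5.3.2 to 5.3.4.

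**The concern.** On the 0 to 3 scale in SAP 5.3.1, a 2-grade improvement takes a moderate participant to none, while a severe participant need only reach mild. The hurdle differs by stratum, so severity plausibly predicts response. The SAP allows for this in the test and not in the estimate or its interval.

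Two things are at stake. A reader may see an interval that excludes zero beside a non-significant p-value, or the reverse, with no rule for which to believe. And where the arms differ in severity mix, the crude difference carries part of that imbalance. Protocol 4.3 says the data will inform dose selection, so the size of the difference matters as much as the p-value.

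**Working it through.** **Inputs from the documents.** 30 active and 10 placebo per cohort; 70% vs 10% response; two-sided 0.05. The stated power reproduces. At 27:9 (Protocol 9.2, 10% dropout) the continuity-corrected approximation gives 0.871 and Fisher's test with doubled one-sided p gives 0.872, against 87%. At 28:9 (SAP 3, 5% dropout) they give 0.877 and 0.883, against 88%.

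**Assumptions.** Rates by severity, cell sizes by stratum, and CMH without continuity correction.

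**Two single-cohort examples (15:5 per stratum).** CMH chi-squared = [Σ(a − nt/N)]² / Σ[nmt(N − t)/(N²(N − 1))], with a active responders, t all responders, n active, m placebo and N = n + m.

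- *A: active 14/15 and 4/15, placebo 3/5 and 0/5.* Excess 1.25 + 1.00 = 2.25; variance 0.503 + 0.632 = 1.135; chi-squared 4.46, p = 0.035. Crude difference 0.60 − 0.30 = 0.30; SE = √(0.6×0.4/30 + 0.3×0.7/10) = 0.170; Wald interval −0.034 to 0.634, which includes zero. The stratified Wald interval, 0.050 to 0.550, agrees with the test.
- *B: active 8/15 and 8/15, placebo 1/5 and 1/5.* Excess 2.50; variance 1.954; chi-squared 3.20, p = 0.074. Crude difference 0.333; SE 0.156; Wald interval 0.028 to 0.639, which excludes zero. The stratified Wald interval is identical, so stratifying alone does not cure this one.

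**How often they disagree.** All outcomes were enumerated with binomial weights. Entries are the share of cohorts in which the interval and the CMH test differ at 0.05. Rates are 20%/50% active and 5%/15% placebo (moderate/severe). Ranges cover different ways of building the stratified Newcombe interval.

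| Active:placebo, moderate; severe | Crude Wald | Stratified Wald | Crude Newcombe | Stratified Newcombe |
|---|---|---|---|---|
| 15:5; 15:5 | 22% | 25% | 5% | 3–5% |
| 16:4; 14:6 | 15% | 24% | 12% | 3–7% |
| 14:6; 16:4 (reverse) | 29% | 25% | 2% | 8–10% |
| Pooled placebo, 18:25; 12:25 | 13% | 2% | 9% | 1–3% |

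At 70% vs 10% in both strata, crude Wald disagrees in 1.2% (30:10) and 2.9% (27:9). At 40% vs 10% (15:5 per stratum) it is 22.8%, and with no effect (5%/15% in both arms) 14.1%. In the first row nearly every conflict is an interval that excludes zero beside p > 0.05. In the pooled row it is the opposite.

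**Shift in the estimate.**
- *Exact 3:1 in each stratum:* crude and Mantel-Haenszel differences are identical.
- *16:4 and 14:6:* active (16×0.20 + 14×0.50)/30 = 0.34; placebo (4×0.05 + 6×0.15)/10 = 0.11; crude 0.23. For the cohort's 20:20 mix the difference is 0.5×0.15 + 0.5×0.35 = 0.25, so crude is 2 points low. With the imbalance reversed it is 2 points high.
- *Pooled placebo, active 60:40 moderate:severe against 50:50:* 0.6×0.20 + 0.4×0.50 = 0.32, less 0.10, gives 0.22. Placebo at the active mix is 0.6×0.05 + 0.4×0.15 = 0.09, giving 0.23. The bias is 1 point. It is 2 points if the pooled placebo were 40:60, since placebo would then be 0.11.

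**Why a score interval settles the conflict.** With Mantel-Haenszel weights w = nm/N, each w(p − q) equals a − nt/N. At zero difference the pooled rate is t/N, and w²(t/N)(1 − t/N)(1/n + 1/m)·N/(N − 1) = nmt(N − t)/(N²(N − 1)). Both are the CMH terms, so a stratified score interval with these weights and the N/(N − 1) factor excludes zero exactly when CMH p < 0.05.

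**The case against.** The choice is deliberate, disclosed and compatible with the protocol. A crude risk difference is a legitimate summary, and the estimand table in SAP 1.1 asks only for response rates by group. A reader might infer that the SAP contradicts itself or the protocol; it does not.

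The 22% is mainly a small-sample Wald problem: stratifying Wald makes agreement no better, and changing the interval type alone removes most of the conflict. It also needs stratum rates that neither document gives. These objections stand, and they set the weight of the point.

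A reader might also infer that ignoring the strata makes the reported SE too large. At 50%/90% vs 5%/15%, the crude formula at the true rates gives √(0.7×0.3/30 + 0.1×0.9/10) = 0.1265 against a true SD of 0.120. But the SE as estimated from the data averages about 0.119, and the crude Wald interval covers 90.7%. The interval is too short, not too long.

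Nor does stratified Newcombe always agree better with the test: with the imbalance reversed, crude Newcombe agrees more often. What remains is that the crude estimate shifts with the imbalance in either direction, and that the pooled comparison has no randomised balance on severity.

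**Conclusion.** The point holds, at minor to moderate weight. The primary p-value and the effect estimate come from different analyses and can contradict each other: in about 1% to 3% of cohorts at the planned effect, and in about 22% at smaller effects that are plausible for low-dose cohorts. Most of that is due to the Wald interval.

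Stratification adds a smaller, separate gain. It corrects a shift of about 2 points if strata fall at 16:4 and 14:6, and about 1 point in the pooled-placebo comparison at a 60:40 against 50:50 mix. These sizes rest on the assumed stratum rates and cell counts.

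It would be too strong to say that the within-cohort estimate is biased as planned: under exact 3:1 in each stratum it equals the stratified one. P-values are nominal, and SAP 5.1 and 5.3.2 class the pooled comparison as a sensitivity analysis, which limits the consequence.

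**What to change.** In SAP 5.3.2, replace the sentence on unstratified differences. Report the Mantel-Haenszel-weighted common risk difference across the two severity strata with a stratified score or Newcombe 95% interval, not Wald. Name the exact construction, since Newcombe versions differ; the score form with Mantel-Haenszel weights matches the CMH test by construction. In SAP 5.3.3, apply the same to the pooled-placebo comparison. Keep crude response rates by arm as description. SAP 5.4.2 then carries the change to the secondary responder endpoints.

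The cost is one or two sentences and a change of procedure option, with no new data and no conflict with the protocol.
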